6.3.2.2 IgG4-RD Responder Index

The IgG4-RD RI is a validated instrument for longitudinal assessment of IgG4-RD disease activity, developed and refined by an international team of IgG4-RD experts specifically to permit structured assessment of response to treatment by clinical investigators (Carruthers et al, 2012; Wallace et al, 2018). The RI captures disease activity and damage in 25 domains, with higher weights for disease manifestations that require urgent treatment or that worsen despite treatment. The RI incorporates an activity score for each organ/site of disease, a score for symptomatic disease at each of these sites, and a score amendment for a need for urgent treatment. Serum IgG4 concentration and presence of organ-specific damage are collected but are not part of the overall RI. Because visit-to-visit consistency is important, whenever possible, the same Investigator should complete the IgG4-RD RI for the same subject across all visits.

Not all results needed to complete the IgG4-RD RI (in particular, labs and imaging) will be available at the time of the subject's visit. Therefore, the investigator may delay completion of the IgG4-RD RI for up to 15 business days of the visit date to permit all results to be considered. All other assessments related to the IgG4-RD RI should be completed on the day of the visit.

6.3.2.3 Cumulative Glucocorticoid Use

Cumulative GC use will be calculated as the total GC dose in mg of prednisone or prednisone equivalent taken for the purpose of IgG4-RD disease control during the RCP.

Clinical Study Protocol VIB0551.P3.S2 - MITIGATE Amendment 9.1, 08AUG2023

Horizon Therapeutics Ireland DAC Inebilizumab IgG4-Related Disease

6.3.3 Safety Assessments

Clinically important abnormalities in vital signs, body weight, physical examination, laboratory parameters, and ECGs will be recorded as AEs or SAEs.

6.3.3.1 Vital Signs, Body Weight, and Physical Examinations

Vital signs, including systolic and diastolic blood pressure (mmHg), pulse rate (beats/min), respiratory rate (breaths/min), body temperature (°C), and body weight (kg), will be measured using clinically acceptable methods and devices as defined in the schedules of assessments and the IP Administration Manual. Subjects should be seated or supine when vital signs are obtained.

Depending on the visit, physical examinations will be either a full examination (excluding rectal and pelvic examinations) or a symptom-driven examination. Examination of the head and neck, including orbits, salivary glands, and lymph nodes, are to be included in both the complete and the symptom-driven physical examinations.

6.3.3.2 Electrocardiogram

A 12-lead ECG will be performed according to the schedule of assessments and procedures. All ECG recordings will be made with the subject in a supine position, having rested in this position for at least 5 minutes before the start of the ECG.

Each ECG will include ventricular heart rate and intervals (PR, RR, QRS, QT, QTc). The Investigator will be responsible for providing an interpretation of the ECG. Clinically significant abnormalities will be recorded as AEs.

6.3.3.3 Pregnancy

Serum β -hCG pregnancy test(s) will be completed for all females during the screening period and urine pregnancy tests will be completed in females of childbearing potential at all subsequent study visits. At visits where an IP infusion will be administered, a negative urine pregnancy test result must be obtained prior to administration of IV IP in female patients capable of pregnancy. Urine pregnancy tests will be performed at the site. Pregnancy in a female subject who has received IP must be reported to the Sponsor within 24 hours of Investigator awareness (Section 8.5.1).

6.3.3.4 Assessment of Adverse Events

For instructions on collecting and reporting AEs, refer to Section 8.

6.3.3.5 Safety Laboratory Assessments

For descriptions of all laboratory assessments, refer to Section 6.3.4.

6.3.3.6 Anti-drug Antibody Assessments

For descriptions of ADA assessments, refer to Section 6.3.7.

6.3.4 Clinical Laboratory Assessments

Blood and urine samples will be collected for laboratory safety tests as specified in the schedules of assessments (Section 6.2). Laboratory testing is described below. For further details regarding laboratory assessments, see the Study Laboratory Manual.

In certain instances, safety laboratory tests may be run in a qualified and licensed local laboratory with prior approval of the sponsor, even where the exclusion criterion specifies use of the central laboratory. Such instances will not be considered protocol deviations.

6.3.4.1 Hematology

The hematology panel will include a complete blood count, with white blood cell count (WBC) and differential (basophils, eosinophils, lymphocytes, monocytes, and neutrophils), hemoglobin, hematocrit, and platelet count.

6.3.4.2 Serum Chemistry

Serum chemistry assessments will include:

- Albumin
- Alkaline phosphatase (ALP)
- Alanine transaminase (ALT)
- Amylase
- Aspartate transaminase (AST)
- Bicarbonate
- Blood urea nitrogen (BUN)
- Calcium
- Chloride
- Creatinine
- Gamma-glutamyl transferase (GGT)
- Glucose (random)
- Hemoglobin A1C (HbA1C)

• Lipase

- Magnesium
- Phosphorus
- Potassium
- Serum to be frozen for possible future safety testing
- Sodium
- Total bilirubin (TBL): (if > 1.5 ULN, indirect and direct bilirubin will be measured)
- Total protein
- Uric acid

Tests for AST, ALT, ALP, and TBL must be conducted concurrently and assessed concurrently.

6.3.4.3 Coagulation Parameters

Coagulation parameters will include prothrombin time, international normalized ratio, and activated partial thromboplastin time.

6.3.4.4 Urinalysis

Urinalysis will evaluate color, appearance, and specific gravity. Standard dipstick analysis, including pH, protein, glucose, blood, and bilirubin, will be performed. Samples with abnormal dipstick will have microscopy performed. Microscopy will include WBC/high power field (HPF) and red blood cell count/HPF.

Urine protein/creatinine ratio calculates the protein/creatinine ratio from a random urine sample to estimate the 24-hour protein excretion as a marker of renal disease.

6.3.4.5 Progressive Multifocal Leukoencephalopathy

PML is a rare, life-threatening CNS infection caused by the JCV (Berger et al, 2013). Although no confirmed cases of PML have been reported following inebilizumab exposure, PML remains a potential risk based on the inebilizumab mechanism of action. In a case of suspected PML, a cerebrospinal fluid sample should be collected to test for JCV by polymerase chain reaction testing using a validated assay in a clinical testing laboratory.

6.3.6 Imaging

All subjects will have had chest, abdomen, and pelvis imaging (CT scans, unless a CT scan is contraindicated) at baseline unless a CT scan or other appropriate imaging (such as, but not limited to, positron emission tomography [PET] scan or MRI) had been performed within the 3 months prior to screening visit and the reading is available. If clinically indicated, imaging (PET scan excluded) may be repeated prior to randomization, to clarify illness, to assess response to GCs, or to ensure exclusion of malignancy. Other imaging is at the discretion of the Investigator.

6.3.7 Immunogenicity Assessments

Blood samples for immunogenicity (ADA to inebilizumab) will be obtained prior to IP administration according to the visits specified in Section 6.2 and will be assessed using a validated immunoassay.

6.4 Discontinuation of Investigational Product, Withdrawal from Study, and Loss to Follow-up

6.4.1 Discontinuation of Investigational Product

IP must be discontinued if the Investigator determines that continuing it would result in a significant safety risk for that subject. The following events require discontinuation of IP:

- 1. Anaphylaxis or a serious hypersensitivity reaction that occurred within 7 days after IV dosing and cannot be attributed to another known allergen exposure (see Appendix B).
- 2. Any AE or significant laboratory abnormality that, in the opinion of the Investigator, Sponsor, or SDMC, warrants discontinuation of dosing.
- 3. Any AE of immune complex disease.
- 4. Any life-threatening (Grade 4) AE.
- 5. Any event of sepsis or febrile neutropenia.
- 6. Any infection listed as either a definite or probable opportunistic infection in Appendix A.
- 7. Any Grade 3 AE with the following exceptions:
 - A Grade 3 AE of flare or exacerbation of IgG4-RD (per protocol, these events are not reported as SAEs as they may represent the primary endpoint of the study)
 - A Grade 3 event that is not an IRR or infection, does not meet any other discontinuation criterion, and for which the SDMC has agreed that IP dosing can continue
- 8. Pregnancy or a decision to become pregnant.
- 9. Malignancy.
- 10. Absolute neutrophil count < 800 cells/µL confirmed by repeat testing.
- 11. Withdrawal of consent for further study participation or for further receipt of IP.
- 12. Receipt of prohibited medication(s) (see Section 7.5.1).
- 13. Determination that the subject was ineligible for study participation and continuation of IP could pose a safety risk to the subject in the judgment of the Investigator or Sponsor.
- 14. Significant noncompliance with the study protocol, as judged by the Investigator or Sponsor.

Severity of AEs will be graded according to the National Cancer Institute Common Terminology Criteria for Adverse Events (CTCAE) (Section 8.1)

Subjects with Grade 3 SAEs should have their AE data reviewed by the Investigator to specifically address whether or not IP should be discontinued or delayed to ensure patient safety, particularly for Grade 3 SAEs of infection (Section 7.1.1.4). The medical monitor(s) and the SDMC are available for discussions regarding suitability of repeat dosing in a subject who has had a Grade 3 SAE.
Clinical Study Protocol	Horizon Therapeutics Ireland DAC
VIB0551.P3.S2 - MITIGATE	Inebilizumab
Amendment 9.1, 08AUG2023	IgG4-Related Disease

The reason(s) for discontinuing IP must be recorded on the appropriate page of the eCRF. If subjects choose to discontinue IP, the reason, such as an AE, lack of efficacy, or other reason, must be recorded in the eCRF.

Subjects who discontinue IP during the RCP should remain in the study and complete all RCP study visits, assessments, and procedures (with the exception of IP administration and associated

unless they have withdrawn consent for study participation or withdrawn consent for specific assessments (if subjects will not agree to return for visits, safety data can be collected by telephone call if subjects agree).

Subjects who discontinue IP during the RCP may be eligible to enroll in the OLP, if they meet criteria outlined in Section 6.2.3.1. Site Investigators will be trained about the importance of retention of subjects through the completion of the RCP, and patients will be informed about the continued scientific importance of their data even if they discontinue study treatment early.

Subjects who do not participate in the OLP, and subjects who discontinue IP during the OLP, will be asked to return to the clinic for a series of visits occurring every six months for a total of two years after their last dose of IP. These post-discontinuation follow-up visits will include a limited set of assessments including CD20+ B cell counts, immunoglobulins levels, concomitant medications, and adverse events. These visits are described in detail in Section 6.2.4, Safety Follow-Up Period.

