6.2.3 Schedule of OLP Assessments and Procedures

6.2.3.1 Eligibility for OLP

Subjects eligible for the OLP must:

- 1. Have completed the RCP Week 52 visit (end of RCP).
- 2. Must not have had IP discontinued for any of the following safety reasons:
 - Anaphylaxis or a serious hypersensitivity reaction that occurred within 7 days after IV dosing and cannot be attributed to another known allergen exposure (see Appendix B).
 - Any adverse event (AE) or significant laboratory abnormality that, in the opinion of the Investigator, Sponsor, or SDMC, warrants discontinuation of dosing.
 - Any life-threatening (Grade 4) infection.
 - Any event of sepsis or febrile neutropenia.
 - Any infection listed as either a definite or probable opportunistic infection in Appendix A.
 - Any Grade 3 IRR.
 - Any Grade 4 serious adverse event (SAE).
 - Pregnancy or a decision to become pregnant.
 - Malignancy.
 - Absolute neutrophil count < 800 cells/ μ L confirmed by repeat testing.
 - Determination that the subject was ineligible for study participation and continuation of IP could pose a safety risk to the subject in the judgment of the Investigator or Sponsor.
 - Significant noncompliance with the study protocol, as judged by the Investigator or Sponsor.
 - Receipt of any B cell-depleting therapy (eg, rituximab, ocrelizumab, obinutuzumab, ofatumumab, commercially available inebilizumab).
- 3. Have completed a 28-day washout period after discontinuation of non-B cell-depleting, non-GC immunosuppressive therapy initiated during the RCP, if relevant.
- 4. Receive Dose 1 in the OLP within the window of 1-38 days after the RCP Week 52 visit (the final visit for the RCP and the first visit for the OLP cannot occur on the same day).
- 5. Have a planned taper of GCs to discontinuation by 8 weeks after OLP Dose 1, if receiving GC at the time of OLP entry.

To maintain the every-6-month dosing of IP, subjects should enroll in the OLP and be dosed as soon as is feasible after completion of the RCP. All SAEs and AEs that occur between the end of the RCP and start of the OLP must be collected at OLP Visit 1. Investigational product discontinuation rules apply during the OLP (Section 6.4.1).

Table 5 summarizes the schedule of procedures for the OLP.

Study Period					Open-Lal	oel Perio	d						
OLP Visit Number	OLP V1	OLP V2	OLP V3, V4	OLP V5	OLP V6, V7	OLP V8	OLP V9, V10	OLP V11	OLP V12, V13	OLP V14	OLP V15, 17, 19, 21	OLP V16, 18, 20,	OLP V22/EDV

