7.1.1.4 Investigational Product Dosing and Administration

Prior to each infusion in the RCP and OLP, the Investigator or other qualified medical personnel must confirm that none of the conditions requiring delay or discontinuation of IP administration are met (Section 6.4.1).

Premedication (from commercial supplies) with a corticosteroid (eg, methylprednisolone 100 mg IV or equivalent), an antihistamine (eg, diphenhydramine 25-50 mg orally or equivalent), and an anti-pyretic (eg, acetaminophen 500-650 mg orally or equivalent) will be administered approximately 30-60 minutes prior to each IP infusion.

Vital signs will be obtained prior to the start of each IP infusion. An experienced and qualified staff member will place the IV access.

The prepared solution will be administered IV via an infusion pump at an incrementally increasing rate through an IV line containing a sterile, low-protein binding 0.2 or 0.22 micron in-line filter according to the schedule in Table 8.

Table 8Infusion Rate for Investigational Product after Dilution in a 250 mL IV
Bag

Elapsed Time (minutes)	Infusion Rate (mL/hour)
0-30	42
31-60	125
61 to end of infusion	333

IV = intravenous.

Clinical Study Protocol	Horizon Therapeutics Ireland DAC
VIB0551.P3.S2 - MITIGATE	Inebilizumab
Amendment 9.1, 08AUG2023	IgG4-Related Disease

Unless an infusion reaction occurs resulting in discontinuation of infusion, the entire infusion bag contents must be administered and the tubing must be flushed with a volume of saline at least as large as that of the tubing to ensure complete delivery of the IP infused at a rate not to exceed 333 mL/hour.

After completion of the infusion, subjects will be observed for at least one hour.

Medically qualified personnel must be immediately available to respond to emergencies during administration of IP. Appropriate drugs and medical equipment to treat acute hypotensive, bronchoconstrictive, or anaphylactic reactions must be immediately available, and study personnel must be trained to recognize and treat these reactions. Additionally, appropriate drugs and medical equipment to treat IRRs must be immediately available, and study personnel must be trained to recognize and treat these reactions.

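### Protocol 6.4.1 gives two rules for Grade 3 SAEs of infection (required stop, or stop-or-delay on review); secondarily, 6.2.3.1 leaves some required-stop events unnamed for OLP entry

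*Protocol*

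**What the plan says.** Protocol 6.4.1 lists 14 events for which stopping IP is required. Item 7 reads "Any Grade 3 AE with the following exceptions". The first exception is IgG4-RD flare. The second is "A Grade 3 event that is not an IRR or infection, does not meet any other discontinuation criterion", provided the SDMC has also agreed to further dosing.

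After the list, a closing paragraph deals with Grade 3 SAEs. The Investigator is to review the data and address "whether or not IP should be discontinued or delayed to ensure patient safety, particularly for Grade 3 SAEs of infection (Section 7.1.1.4". Further dosing after such an event is also left open, since the paragraph names the medical monitors and the SDMC as "available for discussions regarding suitability of repeat dosing in a subject who has had a Grade 3 SAE".

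The cited section, 7.1.1.4, says that before each RCP and OLP infusion the Investigator or other qualified staff "must confirm that none of the conditions requiring delay or discontinuation of IP administration are met (Section 6.4.1".

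On the OLP, 6.4.1 says: "Subjects who discontinue IP during the RCP may be eligible to enroll in the OLP, if they meet criteria outlined in Section 6.2.3.1". Criterion 2 of 6.2.3.1 opens with "Must not have had IP discontinued for any of the following safety reasons" and gives 13 bullets. These include Grade 4 infection, Grade 4 SAE and Grade 3 infusion-related reaction (IRR). They do not include item 3 of 6.4.1, "Any AE of immune complex disease".

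**The concern.** The first matter is a contradiction within one section. For a Grade 3 SAE of infection, the list allows no exception, while the closing paragraph treats delay as an available outcome and singles out infection. Two sites could follow the protocol and handle the same event differently.

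The second is a mismatch between two lists. Section 6.4.1 makes 6.2.3.1 the test for a subject stopped in the RCP, but some events that require a stop are not named there. For those subjects, whether they are dosed in the OLP or go to the safety follow-up period depends on opinion or inference. Both matters bear on subject safety and on uniform conduct across sites.

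**Working it through.** No arithmetic beyond a count applies, so the check sets the passages side by side.

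**Step 1. Grade 3 infection within 6.4.1.**

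| Event | Item 7 | Closing paragraph | Result |
|---|---|---|---|
| Grade 3 infection, serious | Stop required; neither exception applies | Stop or delay addressed on review; repeat dosing open to discussion | Conflict |
| Grade 3 infection, not serious | Stop required; neither exception applies | Not covered (Grade 3 SAEs only) | No conflict |
| Grade 3 SAE, not infection, IRR or flare | Stop required unless the SDMC agrees and no other item is met | Review and discussion | Can be read together |

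**Step 2. Does the cross-reference settle it?** The closing paragraph cites 7.1.1.4, which sends the reader back to 6.4.1 for conditions requiring delay. Neither section sets a condition for delaying a dose because of infection. Delay is mentioned in three other places: active infection at randomization (5.2, criterion 23), vaccination before Dose 1 (Table 3, note b) and an unavoidable delay of Visit 9 (Table 4, note e). None addresses a Grade 3 infection during treatment.

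**Step 3. Map the 14 items of 6.4.1 to the 13 bullets of 6.2.3.1 criterion 2.**

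- Matched: items 1, 2, 5, 6, 8, 9, 10, 13, 14, which is 9.
- Partly matched: items 4, 7, 12, which is 3.
- Not named: items 3 and 11 (withdrawal of consent), which is 2.
- Items: 9 + 3 + 2 = 14. Bullets: 9 (one for each matched item) + 2 (item 4) + 1 (item 7) + 1 (item 12) = 13.

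The gaps that rest on adverse events are in items 3, 4 and 7.

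**Step 4. What is left of those three items.**

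| 6.4.1 item | Named in criterion 2 | Not named |
|---|---|---|
| 3, immune complex disease | Nothing specific | The whole item |
| 4, any Grade 4 AE | Grade 4 infection; Grade 4 SAE | Grade 4 AEs that are neither |
| 7, Grade 3 AE with exceptions | Grade 3 IRR | Other Grade 3 AEs requiring a stop, unless another bullet applies (such as sepsis or an Appendix A infection) |

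The item 4 remainder has a documented example. Section 8.1 keeps IgG4-RD flare out of SAE reporting unless it is fatal or occurs in screening. Item 7 excepts a Grade 3 flare, but item 4 has no flare exception. A Grade 4 flare in the RCP therefore requires a stop, yet is not reported as the Grade 4 SAE that criterion 2 names.

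**Step 5. What else reaches the residual events.**

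- The bullet in criterion 2 for AEs that the Investigator, Sponsor or SDMC considers to warrant stopping. It mirrors item 2, which 6.4.1 lists separately from items 3, 4 and 7.
- The note closing Appendix A, which lets the Investigator treat further infections as exclusionary.
- The check before each infusion in 7.1.1.4.
- The statement in 6.2.3.1 that the 6.4.1 rules apply in the OLP.

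The first two depend on judgment. The last two do not say whether an event that ended RCP dosing still counts at the first OLP dose.

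**The case against.** On the first matter, the best defence is that the list is mandatory and takes precedence, so the closing paragraph serves only Grade 3 SAEs that the SDMC may waive. That works for non-infectious events. It does not work for infection, because the paragraph names infection in particular and item 7 closes the waiver to it. The closing paragraph might also be taken as itself supplying the condition for delay to which 7.1.1.4 refers. On that reading 6.4.1 permits what its own item 7 rules out, so the conflict remains.

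A reader might infer that every Grade 3 infection is affected. The text does not support that, because the closing paragraph is limited to SAEs.

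On the second matter the objection is stronger. A reader might infer that 6.2.3.1 is silent on items 4 and 7. It is not: it names Grade 4 infection, Grade 4 SAE and Grade 3 IRR. Section 8.1 counts life-threatening events, and significant incapacity, as serious, so most Grade 4 AEs should fall under the SAE bullet. Nor must the two lists match, since 6.4.1 expects that some stopped subjects may enter the OLP. The judgment routes in Step 5 would probably exclude many of the residual subjects, and nothing shows that they would be dosed. What stands is that, for these required stops, the protocol does not say whether the RCP event bars OLP dosing.

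**Conclusion.** The first matter holds as an internal contradiction, limited to Grade 3 SAEs of infection. It is a conflict between two safety instructions in current text, not missing detail, and should be fixed.

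The second holds as a request for clarification on three residual groups: immune complex disease; Grade 3 AEs other than IRR that no other bullet covers; and Grade 4 AEs that are neither infections nor SAEs, such as a Grade 4 flare.

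The conclusion rests on reading the 6.4.1 list as mandatory, as its introduction states, and on taking infection in item 7 to include serious and non-serious cases. The documents give no number of affected subjects. A reader might infer harm to the efficacy result. The documents do not support that: subjects who stop IP stay in the RCP, and the primary analysis uses all RCP data under a treatment policy strategy.

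**What to change.** 1. Reconcile 6.4.1 item 7 with the closing paragraph of 6.4.1 and with 7.1.1.4 for Grade 3 SAEs of infection. If any conditions for delaying a dose are intended, say where they are listed.
2. Reconcile 6.2.3.1 criterion 2 with 6.4.1 items 3, 4 and 7. For each residual event, state whether a stop in the RCP bars OLP dosing.

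Which rule applies is for the sponsor's clinicians and the SDMC to decide. The cost is protocol wording only, by amendment or clarification letter. The SAP and the primary analysis do not change.
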